10.5 VITAL SIGNS

Descriptive statistics for systolic blood pressure (mm Hg) diastolic blood pressure (mm Hg), pulse rate (bpm), temperature (°C), height (cm), and weight (kg) will be presented by study visit and treatment group visit for each study part. Also, changes in these vital signs from baseline to each subsequent visit will be tabulated by dose level/treatment group for each study part. Note that height is only collected at Screening and weight is only collected at Screening and at the beginning of each cycle of treatment.

A listing of vital signs will also be provided.

10.6 ELECTROCARDIOGRAMS AND HOLTER MONITORING

Electrocardiogram (ECG) readings and Holter Monitoring are assessed by BioClinica (Princeton, NJ). All patients will have Screening and Cycle 1 (at Day 8) ECG evaluated to have ECG parameters (Heart Rate (bpm), RR (msec), PR (msec), QRS (msec), QT (msec), and QTcF (msec)) collected. The QT data will be corrected using Fridericia correction and calculated as $QTcF = QT/[RR^{(1/3)}]$. Furthermore, an overall assessment of the ECG results on a subject-visit level will be classified as 'Normal', 'Abnormal, Not Clinically Significant', or 'Abnormal, Clinically Significant'.

During PK sampling days (Cycle 1, Day 1 and 15), a subset of patients will have Holter monitoring (12± 2 hours) performed.

For subjects with a clinically significant abnormal ECG in Cycle 1, their ECGs will be conducted at Days 22, 29, 36, 43, and, in patients who continue treatment, every 3 weeks or if clinically indicated thereafter.

Holter ECG analyses will be conducted by BioClinica and are detailed in the Clinipace Worldwide/BioClinica work order. All ECG parameters will be summarized as actual values and as changes from screening/baseline by study visit AND treatment group for each study part; assessments by cohort will only be performed for cohorts of at least 3 subjects.

The primary analysis will be a concentration-response (PK:PD) analysis of QTcF, assuming no hysteresis and a linear relationship between PK and QTc. Secondary analyses will provide summary statistics by time-point and dose for: HR, PR, QRS, QT, and QTcF.

A listing of ECG findings will also be provided.

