11 ADDITIONAL ANALYSES

11.1 PHARMACOKINETIC ANALYSES

Samples for PK analysis of BVD-523 and selected metabolites will be obtained from all Part 1 patients during their first cycle of treatment (Cycle 1). PK samples may also be obtained from additional patients in Part 2 depending on the outcome of initial PK analysis.

At Visit 2 (Baseline) blood samples (3 mL) will be collected prior to dosing, and then at 0.5, 1 (± 5 minutes), 2, 4, 6, 8 (± 10 minutes), and 12 (± 2 hours) post-dose after the administration of the first dose of the first cycle. At Day 15 (Visit 4; at steady-state) blood samples will be collected prior to dosing and then, 0.5, 1, 2, 4, 6, 8, and 12 ± 2 hours post-dose. A single sample will be collected on Day 22 prior to dosing on that day.

For Part 1 subjects, at Visit 2 (Baseline) urine samples will be collected pre-dose. Total urine for the 1–6-hour and 6–12 ± 2 -hour time periods post-dose after the administration of the first dose of the first cycle will also be collected. At Day 15 (Visit 4; at steady-state) urine samples will be collected pre-dose and then for the 1–6-hour and 6–12 ± 2 -hour time periods post-dose. No urine PK samples will be collected for Part 2 subjects.

Below is the list of various PK parameters that will be calculated after Dose 1 (Day 1) and at Steady State (Day 15) using both blood and urine samples:

PK Parameter (plasma)	Description
C_{max}	Peak plasma concentration determined manually by visual inspection of plasma concentration vs. time figures on the untransformed (linear) scale of measurement
t_{max}	Time to reach the peak plasma concentration determined manually by visual inspection of plasma concentration vs. time figures on the untransformed (linear) scale of measurement
AUC_{0-12}	Area under the plasma concentration-time curve from 0 to 12 hours postdose, calculated by linear/log trapezoidal method
AUC_{1-12}	Area under the plasma concentration-time curve from 1 to 12 hours postdose, calculated by linear/log trapezoidal method (for use in calculating CL_r)
AUC_{0-last}	Area under the plasma concentration-time curve from time 0 to time of last observation after dosing calculated by linear/log trapezoidal method

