λ_z	Terminal phase rate constant, determined by linear regression of at least 3 points on the terminal phase of the log-linear plasma concentration-time curve. The correlation coefficient (r^2) for the goodness of the fit of the regression line through the data points has to be 0.85 or higher for the value to be considered reliable. If the WinNonlin data points are not on the linear portion of the terminal slope, the data points will be selected manually prior to calculation of λ_z .
$t_{1/2}$	Terminal half-life, defined as $0.693 (\ln 2)$ divided by λ_z .

PK Parameter (urine)	Description
U ₁₋₆	Amount excreted in urine calculated from Time 1 to 6 hours
U ₁₋₁₂	Cumulative amount excreted in urine calculated from Time 1 to 12 hours
CL _r	Renal clearance, U ₁₋₁₂ divided by AUC ₁₋₁₂
Ae%	Percentage of the dose excreted in the urine, U ₁₋₁₂ divided by the dose and multiplied by 100.

Only AUC_{0-last} will be calculated from the single sample collected at prior to dosing on Day 22.

PK concentration and PK parameters calculated from both blood and urine samples will be provided by Covance. Descriptive statistics [n, arithmetic mean, standard deviation, coefficient of variation (CV), median, minimum, maximum, geometric mean, geometric standard deviation geometric CV] will be used to summarize PK parameters by treatment. For $t_{1/2}$ and t_{max} , regular descriptive statistics and 95% confidence intervals about the arithmetic mean will be calculated, if possible, for each dose, but not geometric mean, geometric standard deviation, and geometric CV. Refer to Pharmacokinetic Analysis Outline (PKAO) for additional details re. the PK analyses.

Listings of PK concentrations (blood and urine) and PK parameters will also be provided.

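### Two SAP derivations fail as written: the QTcF formula takes RR in msec without converting to seconds, and AUC0-last is assigned to a single Day 22 pre-dose sample

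*SAP*

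**What the plan says.** **QTcF.** SAP 10.6 gives the ECG parameters with their units: "RR (msec), PR (msec), QRS (msec), QT (msec), and QTcF (msec)) collected". The next sentence gives the correction: "The QT data will be corrected using Fridericia correction and calculated as $QTcF = QT/[RR^{(1/3", that is, QT over the cube root of RR. The formula carries no unit and no conversion. The same section then uses the result in two ways. First, "All ECG parameters will be summarized as actual values and as changes from screening/baseline by study visit AND treatment group for each study part". Second, "The primary analysis will be a concentration-response (PK:PD) analysis of QTcF", with a linear relationship and no hysteresis assumed.

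**Day 22 AUC.** SAP 11.1 says of sampling: "A single sample will be collected on Day 22 prior to dosing on that day". Protocol 6.9.1 agrees. SAP 11.1 introduces the parameter table with "Below is the list of various PK parameters that will be calculated after Dose 1 (Day 1) and at Steady State (Day 15"), and defines AUC0-last as the area "from time 0 to time of last observation after dosing calculated by linear/log trapezoidal method". After the table it adds that only AUC0-last "will be calculated from the single sample collected at prior to dosing on Day 22".

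**The concern.** In each case the SAP states a rule that gives a wrong or impossible result when followed.

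For QTcF, the stated units and the stated formula cannot both stand. The Fridericia form is right with RR in seconds, but the only unit the SAP gives for RR is msec. The protocol's section on cardiac effects describes a low but observable potential for QT prolongation and commits to QTc monitoring, so the derivation matters for this drug. An absolute QTcF near 40 msec would be noticed. A change or slope that is ten times too small is less conspicuous, and it errs towards false reassurance.

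For Day 22, the SAP promises a parameter that its own definition does not allow. It is also the only derivation the SAP states for that sample.

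**Working it through.** The documents give no numerical result for either derivation, so there is no figure to reproduce. The check applies each rule literally.

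**1. QTcF**

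Inputs from SAP 10.6: QT and RR in msec; formula QT / RR^(1/3). The comparison is QT / (RR/1000)^(1/3). The QT and RR values below are illustrative assumptions, not trial data.

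| QT (msec) | RR (msec) | As printed | RR in seconds | Ratio |
|---|---|---|---|---|
| 360 | 600 | 360/600^(1/3) = 42.7 | 360/0.6^(1/3) = 426.8 | 10.0 |
| 400 | 800 | 400/800^(1/3) = 43.1 | 400/0.8^(1/3) = 430.9 | 10.0 |
| 420 | 1200 | 420/1200^(1/3) = 39.5 | 420/1.2^(1/3) = 395.2 | 10.0 |

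The ratio is always 1000^(1/3) = 10, whatever the QT or heart rate. The printed formula also returns a quantity in msec^(2/3), not msec.

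The intended scale is clear from the protocol, whose inclusion criterion 9 requires QTc below 470 ms. At RR = 1000 msec, the printed formula reaches 470 only if QT = 470 × 10 = 4700 msec.

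Change from screening, for an illustrative move from QT 400/RR 900 to QT 390/RR 800:

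- RR in seconds: 390/0.8^(1/3) − 400/0.9^(1/3) = 420.1 − 414.3 = +5.8 msec.
- As printed: 42.0 − 41.4 = +0.6.

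A slope of QTcF on concentration scales in the same way, so a 10 msec effect would appear as 1.

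**2. AUC0-last on Day 22**

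Sampling times from SAP 11.1:

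| Day | Samples | Post-dose samples | Trapezoids |
|---|---|---|---|
| 1 and 15 (each) | pre-dose, 0.5, 1, 2, 4, 6, 8, 12 h = 8 | 7 | 8 − 1 = 7 |
| 22 | pre-dose = 1 | 0 | 1 − 1 = 0 |

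With no post-dose observation and no interval, the parameter is undefined, or trivially zero.

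Nor can the Day 22 sample serve as the end of the Day 15 curve. At nominal days, 2 × 7 − 1 = 13 further twice-daily doses are scheduled after the Day 15 morning dose and before the Day 22 morning dose.

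The sentence also departs from the scope stated elsewhere. SAP 11.1 ties the parameter list to Day 1 and Day 15. SAP 5.4 defines the PK population by parameters for those two days. Protocol Table 6.2 covers Dose 1 and steady state, and Protocol 6.9.1 labels Day 15 as steady state.

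**The case against.** On QTcF, the best reply is that the SAP names a standard method whose usual printed form is this one with RR in seconds, so the defect is a missing unit rather than a wrong formula. QTcF is also listed among the parameters collected, an ECG vendor reads the ECGs, and the Holter analyses are detailed in a work order that is not among these documents. It may be that nobody will program this line. If somebody did, absolute values near 40 msec would be caught in the first listing. The concentration-QTcF model is primary only within SAP 10.6; QTcF is not a study endpoint, and SAP 6.5 plans no inferential testing.

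Most of this stands as mitigation, and it limits the consequence. It does not repair the text. The unit printed beside the formula is msec, and the section says both that QTcF is collected and that it is calculated, without saying which governs.

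On Day 22, the reply is that an external laboratory supplies the PK parameters and SAP 11.1 refers to a Pharmacokinetic Analysis Outline, also not among these documents, which may contain the intended rule. It may, but it cannot make one pre-dose sample yield an area under the SAP's definition. It is also fair to say that SAP 5.4 defines a population rather than the permitted days, that no table title in SAP Section 14 names a Day 22 AUC, and that the concentration itself is not lost: the SAP lists it, and Protocol 10.3.7 summarizes concentrations by time point.

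**Conclusion.** Both points hold. The printed QTcF formula, with RR in the msec the SAP specifies, gives exactly one tenth of the Fridericia value. Every change from baseline and every concentration slope derived from it is reduced by the same factor. This is conditional on QTcF being derived from the SAP text; values supplied by the vendor may already be correct. The factor of 10 does not depend on the illustrative QT and RR values.

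AUC0-last for Day 22 cannot be computed: there is one sample, none of it post-dose, and no trapezoid. This follows from the SAP's own definition and schedule without further assumption.

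The corrections should be made, but the reach is limited. DLT, MTD, tumor response and sample size are unaffected.

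**What to change.** 1. **SAP 10.6:** state QTcF = QT/(RR/1000)^(1/3), with QT and RR in msec, and say whether QTcF is taken from the ECG vendor or derived from this formula.
2. **SAP 11.1:** delete the Day 22 AUC0-last sentence. State that no AUC is derived for Day 22 and that the Day 22 pre-dose concentration is summarized descriptively, in line with Protocol 10.3.7. This is worth stating because SAP 11.1 applies descriptive statistics to PK parameters and only lists concentrations. A comparison with the Day 15 pre-dose value is optional.

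The cost is one sentence in each section. No new data are needed, and nothing in the conduct of the trial changes.

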10.7 OPHTHALMOLOGY EXAMINATIONS

Ophthalmologic examinations findings include best-corrected visual acuity, visual field examination, intraocular pressure, external eye examination, and dilated funduscopy will be collected at Screening, at study termination, and if clinically indicated.

Descriptive statistics will be used to summarize these ophthalmologic examinations findings. A listing of all ophthalmologic examinations findings will also be provided

10.8 PHYSICAL EXAMINATIONS

Physical examinations will include examination of general appearance; skin; eyes; ears, nose, & throat; head & neck; heart; chest & lungs; abdomen; extremities; back; lymph nodes; musculoskeletal; and neurological. These examinations will be conducted at Screening, Baseline, Days 8, 15, 22, 29, 36, 43, and, in patients who continue treatment, every 3 weeks or if clinically indicated thereafter.

The frequency and percentage of patients with each examination finding ('Normal', 'Abnormal Clinically Significant', 'Abnormal Not Clinically Significant', and 'Not Done') will be tabulated for each body system by study visit and dose level/treatment group for each study part.

A listing of physical examination findings will be presented.

11 ADDITIONAL ANALYSES

11.1 PHARMACOKINETIC ANALYSES

Samples for PK analysis of BVD-523 and selected metabolites will be obtained from all Part 1 patients during their first cycle of treatment (Cycle 1). PK samples may also be obtained from additional patients in Part 2 depending on the outcome of initial PK analysis.

At Visit 2 (Baseline) blood samples (3 mL) will be collected prior to dosing, and then at 0.5, 1 (± 5 minutes), 2, 4, 6, 8 (± 10 minutes), and 12 (± 2 hours) post-dose after the administration of the first dose of the first cycle. At Day 15 (Visit 4; at steady-state) blood samples will be collected prior to dosing and then, 0.5, 1, 2, 4, 6, 8, and 12 ± 2 hours post-dose. A single sample will be collected on Day 22 prior to dosing on that day.

For Part 1 subjects, at Visit 2 (Baseline) urine samples will be collected pre-dose. Total urine for the 1–6-hour and 6–12 ± 2 -hour time periods post-dose after the administration of the first dose of the first cycle will also be collected. At Day 15 (Visit 4; at steady-state) urine samples will be collected pre-dose and then for the 1–6-hour and 6–12 ± 2 -hour time periods post-dose. No urine PK samples will be collected for Part 2 subjects.

Below is the list of various PK parameters that will be calculated after Dose 1 (Day 1) and at Steady State (Day 15) using both blood and urine samples:

PK Parameter (plasma)	Description
C_{max}	Peak plasma concentration determined manually by visual inspection of plasma concentration vs. time figures on the untransformed (linear) scale of measurement
t_{max}	Time to reach the peak plasma concentration determined manually by visual inspection of plasma concentration vs. time figures on the untransformed (linear) scale of measurement
AUC_{0-12}	Area under the plasma concentration-time curve from 0 to 12 hours postdose, calculated by linear/log trapezoidal method
AUC_{1-12}	Area under the plasma concentration-time curve from 1 to 12 hours postdose, calculated by linear/log trapezoidal method (for use in calculating CL_r)
AUC_{0-last}	Area under the plasma concentration-time curve from time 0 to time of last observation after dosing calculated by linear/log trapezoidal method

λ_z	Terminal phase rate constant, determined by linear regression of at least 3 points on the terminal phase of the log-linear plasma concentration-time curve. The correlation coefficient (r^2) for the goodness of the fit of the regression line through the data points has to be 0.85 or higher for the value to be considered reliable. If the WinNonlin data points are not on the linear portion of the terminal slope, the data points will be selected manually prior to calculation of λ_z .
$t_{1/2}$	Terminal half-life, defined as $0.693 (\ln 2)$ divided by λ_z .

PK Parameter (urine)	Description
U ₁₋₆	Amount excreted in urine calculated from Time 1 to 6 hours
U ₁₋₁₂	Cumulative amount excreted in urine calculated from Time 1 to 12 hours
CL _r	Renal clearance, U ₁₋₁₂ divided by AUC ₁₋₁₂
Ae%	Percentage of the dose excreted in the urine, U ₁₋₁₂ divided by the dose and multiplied by 100.

Only AUC_{0-last} will be calculated from the single sample collected at prior to dosing on Day 22.

PK concentration and PK parameters calculated from both blood and urine samples will be provided by Covance. Descriptive statistics [n, arithmetic mean, standard deviation, coefficient of variation (CV), median, minimum, maximum, geometric mean, geometric standard deviation geometric CV] will be used to summarize PK parameters by treatment. For $t_{1/2}$ and t_{max} , regular descriptive statistics and 95% confidence intervals about the arithmetic mean will be calculated, if possible, for each dose, but not geometric mean, geometric standard deviation, and geometric CV. Refer to Pharmacokinetic Analysis Outline (PKAO) for additional details re. the PK analyses.

Listings of PK concentrations (blood and urine) and PK parameters will also be provided.

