##### 3.1.2 Study Design

This clinical study comprises 2 parts:

- Part 1: Dose-escalation Phase
- Part 2: Cohort Expansion Phase

Part 1 – Dose-escalation Phase: An accelerated dose escalation plan will be used to establish dose limiting toxicities (DLT), maximum tolerated dose (MTD), and the recommended Phase 2 dose (RP2D). One to 6 patients per treatment cohort will be assigned to receive sequentially higher oral doses of BVD-523 on a twice daily schedule (b.i.d.) for 21 days (a “Cycle”), starting at a dose of 10 mg twice daily. Patients will receive twice-daily oral doses of BVD-523 until disease progression, unacceptable toxicity, or a clinical observation satisfying another withdrawal criterion is noted. Treatment cycles will occur consecutively without interruption, except when necessary to manage toxicities.

Patients with advanced-stage solid tumors only (no hematological malignancies) will be enrolled in the dose-escalation phase of the study. The study will initially be conducted as an accelerated single patient design, followed by a standard 3 + 3 design, informed by the

accrued safety experience throughout the study (see Table 3.2 below). All dose-escalation decisions will be based on Cycle 1 safety data.

In the accelerated single patient phase, 1 patient will be enrolled in a cohort and an evaluation of dose escalation will take place after the patient has completed the 21-day treatment cycle. If the patient exhibits no Grade 2 or greater adverse events, dose escalation in a 100% increment and enrollment will continue with a single patient per cohort. However, when one patient experiences a  $\geq$  Grade 2 toxicity (excluding alopecia or diarrhea), this cohort and subsequent cohorts will be expanded to at least 3 patients each following the classic 3 + 3 design and dose escalation increments will be reduced from 100% to a maximum of 50%, as determined by discussion with the Clinical Investigators, the Medical Monitor, and the Sponsor. Doses will not be escalated unless the patient(s) receiving the highest current dose has been observed for at least 3 weeks.

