## **4 SELECTION OF PATIENTS**

### **4.1 NUMBER OF PATIENTS**

In this Phase 1 study up to 40 patients with advanced solid tumors will be enrolled in Part 1. One to six patients per treatment cohort will be assigned to receive sequentially higher oral doses of BVD-523.

The purpose of Part 2 of this first in human research is to document that there is some evidence of a response. Upon completion of Part 1 of this study, up to approximately 105 evaluable patients with certain cancer types and/or characterized genetics will be assigned to 1 of 7 treatment arms and treated with the RP2D determined in Part 1 (which may be the same or lower than the MTD). The observation of DLTs in more than 33% of patients in any Part 2 cohort with at least 6 patients enrolled at any time during Part 2 will trigger temporary stopping of patient enrollment and revision of the definition of the MTD and potentially RP2D in the specific cohort. Subsequent patients will be treated with a dose lower than the initial MTD and this dose will be determined in discussion with the Clinical Investigators, the Medical Monitor, and the Sponsor.

Enrollment of up to 15 evaluable patients in each cohort provides an 80% probability of seeing at least one positive response if the true response rate is at least 10%. Allowing for a low response rate in these patient cohorts is appropriate based on unmet medical need.

In Part 2 of the study, patients who withdraw at any time preceding the 1st protocol-specified tumor measurement evaluation at the end of Cycle 2 (except for study drug-related AE) will be replaced.

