## 6.9 PHARMACOKINETIC PROCEDURES

### 6.9.1 Blood Sampling and Processing

In Part 1, samples for PK analysis of BVD-523 and selected metabolites will be obtained from all patients during their first cycle of treatment (Cycle 1). In Part 2, samples for PK analysis of BVD-523 and selected metabolites will be obtained from all patients during their first cycle of treatment (Cycle 1) until the sponsor determines sampling will be discontinued based on accumulated patient experience. Additional PK samples may also be obtained in the event of an SAE, AE, or intra-patient dose-change at the Investigator's or sponsor's request.

At Visit 2 (Baseline) blood samples will be collected prior to dosing, and then at 0.5, 1 ( $\pm 5$  minutes), 2, 4, 6, 8 ( $\pm 10$  minutes), and 12 hours ( $\pm 2$  hours) post-dose after the administration of the first dose of the first cycle. At Day 15 (Visit 4; at steady-state) blood samples will be collected prior to dosing and then 0.5, 1 ( $\pm 5$  minutes), 2, 4, 6, 8 ( $\pm 10$  minutes), and 12 hours ( $\pm 2$  hours) post-dose. A single sample will be collected on Day 22 prior to dosing on that day. Comprehensive information on blood sample acquisition, handling and storage are to be found in the Study Manual. Sample tube labels include the patient identification number/protocol code, sample number and visit number.

For storage and shipping instructions refer to Study Manual. The analytical laboratory will measure plasma concentrations of BVD-523 using a validated method.

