3 STUDY DESIGN

3.1 OVERALL STUDY DESIGN

This is an open-label, multi-center Phase 1 study to assess the safety, pharmacokinetics, and pharmacodynamics of escalating doses of BVD-523 in patients with advanced malignancies. It will be conducted at up to 15 sites. This clinical study comprises 2 parts: Part 1: Dose-escalation Phase and Part 2: Cohort Expansion Phase.

Part 1: Dose-escalation Phase, An accelerated dose escalation plan will be used to establish DLT, MTD, and the RP2D. One to 6 patients per treatment cohort will be assigned to receive sequentially higher oral doses of BVD-523 on a twice daily schedule (b.i.d.) for 21 days (a “Cycle”), starting at a dose of 10 mg twice daily. Patients will receive twice-daily oral doses of BVD-523 until disease progression, unacceptable toxicity, or a clinical observation satisfying another withdrawal criterion is noted. Treatment cycles will occur consecutively without interruption, except when necessary to manage toxicities. Up to 40 patients will be enrolled in Part 1. Patients with advanced-stage solid tumors only (no hematological malignancies) will be enrolled in the dose-escalation phase of the study. The study will initially be conducted as an accelerated single patient cohorts design, followed by a standard 3 + 3 design, informed by the accrued safety experience throughout the study (see Table 1 below). All dose-escalation decisions will be based on Cycle 1 safety data. Patients who withdraw at any time preceding the last visit of Cycle 1 (Day 22) will constitute an early discontinuation and must be replaced in order to ensure proper data accrual for dose escalation decisions. A patient who experiences a DLT in Course 1 and withdraws before Day 22 either because of the toxicity or otherwise, will nonetheless have that DLT counted in the assessment of potential cohort expansion and/or dose escalation. Doses will not be escalated unless the patient(s) receiving the highest current dose has been observed for at least 3 weeks. No intra-patient dose escalation was permitted under the original protocol or the first two amendments. Starting under amendment three, intra-patient dose escalations were allowed; see protocol for details.

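### SAP 11.1 plans confidence intervals only for tmax and half-life, on the arithmetic mean, which suits small cohorts poorly, and lists none for Cmax, AUC or renal clearance (minor)

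*SAP*

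**What the plan says.** SAP 11.1 gives PK parameters in general a list of descriptive statistics that runs from n and the arithmetic mean to "geometric mean, geometric standard deviation geometric CV] will be used to summarize PK parameters by treatment". No confidence interval is in that list. Half-life and tmax are then treated separately: "95% confidence intervals about the arithmetic mean will be calculated, if possible, for each dose, but not geometric mean". The same sentence also drops the geometric SD and geometric CV for these two. A pointer follows: "Refer to Pharmacokinetic Analysis Outline (PKAO) for additional details re. the PK analyses".

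tmax is defined as "Time to reach the peak plasma concentration determined manually by visual inspection of plasma concentration vs. time figures". The planned post-dose sampling times are 0.5, 1, 2, 4, 6, 8 and 12 hours. Half-life is defined as 0.693 divided by lambda-z. Lambda-z is not among the exceptions, so it keeps its geometric statistics.

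On cohort size, Protocol 3.1.2 says of Part 1: "One to 6 patients per treatment cohort will be assigned to receive sequentially higher oral doses". Part 2 has seven groups of up to 15, all treated at the RP2D. Protocol 6.9.1 collects Cycle 1 PK from all Part 2 patients "until the sponsor determines sampling will be discontinued based on accumulated patient experience"; SAP 11.1 is more conditional and says only that Part 2 samples may be taken. SAP 6.5 plans no inferential testing.

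**The concern.** The two parameters that receive an interval are the two for which a t-interval about the arithmetic mean fits least well. tmax is discrete, unevenly spaced and probably skewed. Half-life is a reciprocal of an estimated rate and is usually right-skewed. The exposure measures, for which a log-scale interval is the natural choice, get none.

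There is also an internal mismatch that needs no distributional assumption. Since log(t½) = log(0.693) − log(λz), half-life and lambda-z carry the same information on the log scale. The SAP summarizes one with geometric statistics and withholds them from the other.

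What is at stake is reporting. Some small-cohort tables would show negative times or intervals of zero width, and the tables would give an interval for tmax but not for exposure.

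**Working it through.** The documents state no numerical figure on this point, so there is nothing of the plan's own to reproduce. They also give no between-patient CV and no tmax distribution. Both are assumed below, and ranges are shown.

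**Interval as planned.** Mean ± t(0.975, n−1)·SD/√n. The multiplier t/√n on the SD is 8.98 at n=2, 2.48 at n=3, 1.59 at n=4, 1.05 at n=6 and 0.55 at n=15. At n=1 it is undefined.

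*Illustration.* For three patients with tmax of 1, 2 and 4 h, the mean is 2.33 and the SD 1.53. The half-width is 2.48 × 1.53 = 3.79, so the interval runs from −1.46 to 6.13 h.

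**tmax.** I assumed two distributions on the times 0.5, 1, 2, 4, 6, 8 h:
- D1: .05, .20, .40, .25, .07, .03 (mean 2.685 h)
- D2: .02, .13, .45, .30, .07, .03 (mean 2.90 h)

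I simulated 200,000 cohorts per case:

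| n | Coverage D1 / D2 | Negative lower limit D1 / D2 | Zero width D1 / D2 |
|---|---|---|---|
| 3 | 90% / 85% | 71% / 65% | 9% / 12% |
| 4 | 82% / 85% | 39% / 27% | 3% / 5% |
| 6 | 92% / 95% | 4% / 1% | under 1% |
| 15 | 93% / 94% | 0% | 0% |

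The zero-width rate can be checked by hand as Σpᵢⁿ. For D1 at n=3: .000125 + .008 + .064 + .015625 + .000343 + .000027 = .088. For D2 the sum is .121.

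*Sensitivity.* Three other assumed shapes gave coverage of 76% to 88% and negative limits in 52% to 80% of cohorts at n=3. At n=6 the negative rate was 0% and 5% for two of them. The third, with 5% of patients peaking at 12 h, still had 32% negative limits at n=6 and coverage of 87%, rising to 89% at n=15. How quickly the fault fades therefore depends on the right tail.

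**Half-life.** Assumed lognormal, with log-scale SD σ = √ln(1+CV²): 0.294, 0.472 and 0.703 at CV 30%, 50% and 80%. Results for the planned interval about the arithmetic mean:

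| CV | Coverage, n=3 to 6 | Negative lower limit, n=3 | Negative lower limit, n=6 |
|---|---|---|---|
| 30% | 94% | 14% | 0% |
| 50% | 92% to 93% | 46% | 0.6% |
| 80% | 88% to 90% | 70% | 10% |

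**Log-scale alternative.** The limits are the geometric mean multiplied and divided by exp(t·σ/√n). For example, at n=3 and CV 50%: exp(2.484 × 0.472) = 3.23.

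| n | CV 30% | CV 50% | CV 80% |
|---|---|---|---|
| 3 | 2.07 | 3.23 | 5.74 |
| 6 | 1.36 | 1.64 | 2.09 |
| 15 | 1.18 | 1.30 | 1.48 |

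Under lognormality, coverage is 95% at every n from 2 upward, and the limits cannot be negative. At n=2 the factor is already 14 at CV 30%, which tells the reader nothing.

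**The case against.** The strongest reply is that little harm follows. PK is secondary, no test is planned, and no rule uses these intervals. For Cmax and AUC the SAP already reports n, geometric mean and geometric SD, from which a log-scale interval can be computed, and individual values are listed. Even the geometric mean half-life can be recovered as 0.693 divided by that of lambda-z, if the same patients contribute. The median, minimum and maximum of tmax are already among the regular descriptive statistics. All of this stands and is why the point is minor.

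Two further replies have some force. The documents allow sampling windows and do not say whether tmax uses nominal or actual times; with actual times, exact ties and zero-width intervals would be rarer. And the PK analysis outline might set a minimum n or add intervals. But it is cited for additional detail and was not supplied, so it cannot be presumed to reverse an explicit SAP statement.

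A reader might infer that the planned intervals are invalid throughout cohorts of 1 to 6, or that every cohort of 3 to 6 will show negative times. The documents and the figures do not support that. At n=1 the SAP's own proviso covers the case. At n=6 negative tmax limits fall to 1% to 4% under D1 and D2, and half-life coverage is only modestly low.

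A reader might also infer that exposure at the RP2D is left without any statement of precision, or that Cmax and AUC are what the RP2D rests on. Neither follows. Spread and geometric statistics are planned. Protocol 3.1.4.3 says only that PK observations may be part of the rationale, and names no parameter.

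**Conclusion.** The point holds as a minor one. The mean-based interval for tmax is poorly suited to cohorts of 2 to 4 patients, where coverage and limits are clearly poor under every distribution tried. By n=6 the fault has largely gone unless the right tail is heavy. For half-life the fault is modest under-coverage plus impossible lower limits in the smallest cohorts, and the handling is inconsistent with that of lambda-z. The absence of intervals for Cmax, AUC and renal clearance is a gap in presentation, since the ingredients are reported.

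The log-scale interval is not a cure for small samples: it is informative mainly from about six patients and, for plasma parameters, in Part 2. The sizes rest on assumed CVs of 30% to 80%, lognormal half-life and assumed tmax distributions. No dose decision, safety rule or conclusion changes.

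**What to change.** In SAP 11.1:
- Report tmax as median, minimum and maximum, and delete its interval about the mean.
- Report half-life as a geometric mean with a 95% interval computed on the log scale and back-transformed.
- Give the same log-scale interval for Cmax, AUC0-12 and renal clearance. For renal clearance this applies to Part 1 only, since no urine PK is collected in Part 2.
- Replace the open-ended proviso with a stated minimum n. Three is workable if the SAP notes that the limits are then a factor of about 2.1 to 5.7 either way; a higher threshold is also defensible.
- Say whether Part 2 intervals are by group or pooled at the RP2D. SAP 2.2 defines Part 2 treatment groups as Groups 1 to 7, while the interval is planned by dose.
- Bring the PK analysis outline into line.

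The cost is SAP wording and a change to the PK parameter table shells (Tables 14.4.1 and 14.4.2 in Part I, 14.4.1 in Part II). No new data are needed. The drawback is that small-cohort intervals will be wide, though that width reflects the information available.
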